11.5 Novartis and GlaxoSmithKline Notification by Investigator

11.5.1 Serious Adverse Event Reporting Requirements

All events meeting the criteria for Serious Adverse Event (see Section 11.2.2) that occur after the start of the initial dose of study treatment, during treatment, or within 30 days of the last dose of treatment must be reported as serious adverse events.

The participating investigator must report each serious adverse event, regardless attribution, to the Principal Investigator (or Protocol Chair) within 24 hours of learning of the occurrence. In the event that the participating investigator does not become aware of the serious adverse event immediately (e.g., participant sought treatment elsewhere), the participating investigator is to report the event within 24 hours after learning of it and document the time of his or her first awareness of the adverse event.

Within the following 24-48 hours, the participating investigator must provide follow-up information on the serious adverse event. Follow-up information should describe whether the event has resolved or continues, if and how the event was treated, and whether the participant will continue or discontinue study participation. The principal investigator has the obligation to report all serious adverse events to the FDA, IRB, Novartis Pharmaceuticals Drug Safety and Epidemiology Department (DS&E), and Glaxo-Smithkline. All events reported to the FDA by the investigator are to be filed utilizing the Form FDA 3500A (MedWatch Form). **All events must be reported to both Novartis Pharmaceuticals DS&E Department [by [contact])], and to GlaxoSmithkline [by e-mail to [contact] and [contact] OR fax to US-Case Management Group ([contact]) and [name] ([contact]) within 24 hours of learning of the event's occurrence.** This includes serious, related, labeled (expected) and serious, related, unlabeled (unexpected) adverse experiences. All deaths during treatment or within 30 days following completion of active protocol therapy must be reported within 5 working days. Any serious adverse event occurring after the patient has started the first dose of study treatment and until 30 days after the patient has stopped study participation must be reported. This includes the period in which the study protocol interferes with the standard medical treatment given to a patient (e.g. treatment withdrawal during washout period, change in treatment to a fixed dose of concomitant medication). Serious adverse events occurring more than 30 days after study discontinuation need only be reported if a relationship to the GlaxoSmithkline or Novartis study drugs is suspected.

If the SAE is not previously documented in the everolimus Investigator Brochure or Package Insert (new occurrence) and is thought to be related to the Novartis study drug, a DS&E associate may urgently require further information from the investigator for Health Authority reporting. Novartis may need to issue an Investigator Notification (IN), to inform all investigators involved in any study with the same drug that this SAE has been reported. Suspected Unexpected Serious Adverse Reactions (SUSARs) will be collected and reported to the competent authorities and relevant ethics committees in accordance with Directive 2001/20/EC or as per national regulatory requirements in participating countries.

For Concomitant Medications, all serious adverse experiences will be forwarded to the product manufacturer by the investigator.

11.5.2 Non-Serious Adverse Event Reporting Requirements

Non-serious adverse events will be reported to the Principal Investigator (or Protocol Chair) on the toxicity Case Report Forms.

11.6 Institutional Review Board (IRB) Notification by Investigator

The participating investigator will report all adverse events and serious adverse events to the Principal Investigator (or Protocol Chair) and to the IRB according to the local IRB's policies and procedures in reporting adverse events.

In the event of a multi-center study, the Principal Investigator (or Protocol Chair) will report adverse events and serious adverse events from all participating sites to the DFCI IRB according to the IRB's policies and procedures in reporting adverse events.

11.7 Food and Drug Administration (FDA) Notification by Sponsor-Investigator

If this study is not IND-exempt, the Sponsor-Investigator will report to the FDA any adverse event that is serious, unexpected and reasonably related (i.e., possible, probable, definite) to the study treatment.

Unexpected fatal or life-threatening experiences associated with the use of the study treatment will be reported to FDA as soon as possible but in no event later than 7 calendar days after initial receipt of the information.

All other serious unexpected experiences associated with the use of the study treatment will be reported to FDA as soon as possible but in no event later than 15 calendar days after initial receipt of the information.

Events will be reported to the FDA by telephone ([name]) or by fax ([name]) using Form FDA 3500A (Mandatory Reporting Form for investigational

agents) or FDA Form 3500 (Voluntary Reporting Form for commercial agents). Forms are available at <http://www.fda.gov/medwatch/getforms.htm>.

11.8 Hospital Risk Management Notification by Investigator

The participating investigator will report to the Principal Investigator (or Protocol Chair) and to local Risk Management any subject safety reports or sentinel events that require reporting according to institutional policy.

12. DATA AND SAFETY MONITORING

12.1 Data Reporting

12.1.1 Method

The QACT will collect, manage, and monitor data for this study.

12.1.2 Data Submission

The schedule for completion and submission of case report forms (paper or electronic) to the QACT is as follows:

Form	Submission Timeline
Eligibility Checklist	Complete prior to registration with QACT
On Study Form	Within 14 days of registration
Baseline Assessment Form	Within 14 days of registration
Treatment Form	Within 10 days of the last day of the cycle
Adverse Event Report Form	Within 10 days of the last day of the cycle
Response Assessment Form	Within 10 days of the completion of the cycle required for response evaluation
Off Treatment/Off Study Form	Within 14 days of completing treatment or being taken off study for any reason
Follow up/Survival Form	Within 14 days of the protocol defined follow up visit date or call

12.2 Safety Meetings

There will be monthly conference calls between the research team at the DF/HCC and the research team at Memorial Sloan-Kettering Cancer Center during the expansion phase of the trial to monitor safety and accrual. The attendee's for this will routinely include the principal investigators (or their designees), research coordinators, Research Nurses, and, as needed, investigational pharmacists. In addition, input during these teleconferences may be obtained from the clinical development teams both at Novartis and GlaxoSmithKline, as needed.

The DF/HCC Data and Safety Monitoring Committee (DSMC) will review and monitor toxicity and accrual data from this trial. The committee is composed of clinical specialists with experience in oncology and who have no direct relationship with the study. Information that raises any questions about participant safety will be addressed with the Principal Investigator and study team.

The DSMC will meet quarterly and/or more often if required to review toxicity and accrual data. Information to be provided to the committee may include: up-to-date participant accrual; current dose level information; DLT information; all grade 2 or higher unexpected adverse events that have been reported; summary of all deaths occurring within 30 days for Phase I or II protocols; for gene transfer protocols, summary of all deaths while being treated and during active follow-up; any response information; audit results, and a summary provided by the study team. Other information (e.g. scans, laboratory values) will be provided upon request.

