Nine patients were enrolled in the phase I portion of this study. Two patients on dose level 0 (pazopanib 600 mg daily and everolimus 5 mg daily) experienced dose limiting toxicities (grade 3 rash and pruritus and grade 3 thrombocytopenia requiring a dose reduction). Therefore, three patients were treated at dose level -1 per protocol. None of these three patients experienced a protocol-defined dose-limiting toxicity. Therefore, another three patients were treated at dose level -1 (pazopanib 400 mg daily and everolimus 5 mg daily) without any dose-limiting toxicities. Therefore, per protocol, dose level -1 was defined as the maximum tolerated dose.

Toxicity	Maximum Grade			
	G1	G2	G3	G4
Febrile neutropenia	-	-	1	-
Neutropenia	1	-	-	-
Thrombocytopenia	3	1	1	-

Hematologic toxicities (see table above) included febrile neutropenia (11%), neutropenia (11%), thrombocytopenia (56%), and anemia (36%). Grade 3 febrile neutropenia and thrombocytopenia each occurred in 1 patient. Non-hematologic toxicities were varied, though many were expected based on the known toxicities of everolimus and pazopanib. One patient did experience a grade 3 pneumothorax, which was possibly related to study therapy. Other non-hematologic toxicities included anorexia (11%), bone pain (11%), diarrhea (22%, 11% G3), fatigue (56%), dysgeusia (11%), headache (11%), hypertension (22%), mucositis (33%), musculoskeletal (muscle stiffness after prolonged periods of sitting, 11%), nausea (44%), palmo-plantar erythrodysesthesia syndrome (11%), pneumonia (11% G3), pruritus (11% G3), rash (33%, 11% G3), vomiting (33%), and weight loss (11%). Toxicities noted in laboratory evaluations were generally consistent with what is expected with both agents administered separately. G3 and 4 laboratory toxicities included increased ALT, hypophosphatemia, and hypouricemia each in 1 patient, and increased lipase in 2 patients.

Treatment was generally well tolerated at the MTD. Two of 6 patients came off treatment after 2 cycles because of toxicity. The others stopped treatment due to disease progression or physician decision.

Antitumor activity

Encouraging antitumor activity was noted in the bladder cancer patients treated on pazopanib and everolimus. Of five urothelial cancer patients evaluable, 3 had stable disease for 4 months, 4 months and 5.5 months respectively. One patient had a complete response which lasted 14 months.

Tumor type	(n)	Best objective response

Bladder	5	3 SD, 1CR, 1 NE

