5.4 Definition of Dose-Limiting Toxicity

5.4.1 Dose escalation rules

General rules:

- Initial dose is dose level 0 for this trial
- All patients in a dose cohort will complete 28 days (1 cycle) of combination treatment prior to the treatment of any patient at a higher dose level.
- If a patient does not complete the 28 days of treatment for reasons that are clearly not adverse events related to treatment, then that patient will be replaced, up to three per dose level.
- If more than three patients need to be replaced on a dose level, then the reasons will be re-evaluated before continuing.
- There will be no intrapatient dose escalation.
- To determine that a subject has received study treatment without experiencing DLT, the subject must have missed no more than 5 days of dosing during cycle 1, either nonconsecutively or consecutively.

Pazopanib and everolimus doses will be escalated according to the following standard 3+3 dose escalation rules:

1. If 0 of 3 patients in a cohort experience dose limiting toxicities, then the next cohort of 3 patients will be treated at the next higher dose level.
2. If 1 of 3 patients in a cohort experiences a DLT then the cohort will be expanded to treat an additional three patients. If only one of 6 patients experiences a DLT, then the next cohort of patients will be treated at the next higher dose level.
3. If two or more patients in a cohort experience a DLT, then the MTD has been exceeded. The previous dose level will be considered the MTD. If only 3 patients were treated at the previous dose level, an additional three patients will be treated at that dose level to confirm the MTD.
4. If the doses of both drugs are escalated to dose level 2 with 0 of 3 or 1 out of 6 patients experiencing a DLT, then this will be considered the recommended Phase II dose (RP2D) for the expansion cohort.
5. If the MTD is exceeded on dose level 0, then a de-escalation cohort to dose level -1 will be enrolled. Up to six patients will be treated at this dose level. If one or fewer of six patients experiences a DLT, then this will be the RP2D. If two or more patients experience a DLT on dose level -1, then the combination will be deemed not feasible and the study will be closed.
6. If the MTD is exceeded on dose level 2, then a de-escalation level will be accrued (dose level 2A). If 0 of 3 or 1 out of 6 patients experience a DLT on dose level 2A,

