5.4.2 Definition of a DLT

Dose-limiting toxicity (DLT) is based on the CTEP Active Version of the NCI Common Terminology Criteria for Adverse Events (CTCAE v4.0).

For the purposes of Phase I dose escalation, a DLT will be defined as toxicity occurring within the first 28 days of combination therapy related to therapy that meets the criteria spelled out below:

1. Grade 3 or 4 non-hematologic toxicity excluding:
 - Toxicity attributed to underlying malignancy
 - Nausea/vomiting controlled with antiemetics
 - Grade 3 hypertension that resolves to $\leq 150/90$ within 7 days of adjustment or addition of oral blood pressure medications.
 - a. Hypertension that requires admission to the hospital or intravenous medication for control will be considered a DLT.
 - b. Grade 3 or greater hypertension that does not respond to adjustment or addition of oral blood pressure medicines to $\leq 150/90$ within 7 days from blood pressure medication modification will be considered a DLT.
 - Grade 3 asymptomatic, clinically insignificant laboratory abnormalities, including LDH, alkaline phosphatase due to bone metastases, and asymptomatic hypophosphatemia
2. Hematologic toxicity defined as:
 1. Grade 4 thrombocytopenia or grade 3 thrombocytopenia with bleeding
 2. Grade 4 neutropenia which persists for >7 days
 3. Grade 4 neutropenia associated with fever $>38.5^{\circ}\text{C}$
 4. Excludes lymphopenia or anemia of any grade
3. Removal of a patient from therapy due to toxicity attributable to treatment
4. Patients who miss more than 5 days of the planned doses for drug-related intolerable grade 2 toxicity will be considered to have experienced a DLT. During cycle 1, patients who miss fewer than 5 days of dosing for drug-related toxicities that do not immediately meet the criteria for DLT must recover to \leq grade 1 within two weeks, or they will be considered to have experienced DLT.
5. Toxicity related to therapy severe enough to require a dose-reduction

Management and dose modifications associated with the above adverse events are outlined in Section 6 (Expected Toxicities and Dosing Delays/Dose Modifications).

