A reduction in blood cell counts is frequent when everolimus therapy is initiated. Without clinical significance and infrequently, anemia and thrombocytopenia have been reported. In heavily pretreated patients with aggressive lymphoma, the incidence of grade 3 anemia, neutropenia, and thrombocytopenia was reported to be 11%, 16%, and 30%, respectively. Serious, suspected drug-related hemorrhages have been exceptional. Nevertheless, everolimus should be considered as predisposing patients to hemorrhage, potentially fatal, should they develop severe drug-related thrombocytopenia.

Discrete, reversible changes in liver enzymes have been found to occur in numerous patients during treatment with everolimus in oncology clinical studies, and in a study in rheumatoid arthritis. In oncology studies, these changes may be evident only in patients without severe underlying morbidity. The increase in transaminase's (AST and ALT) generally appears after 4 weeks of treatment. In all but a few cases it does not exceed Grade 1 ($\leq 2.5 \times$ institution ULN).

Similarly, mild increases in alkaline phosphatases can coexist. Spontaneous corrections or intermittent correction with continued treatment can occur. Serum bilirubin is not increased. In studies of patients with advanced cancers, clinically relevant changes in liver enzymes have been invariably associated with the presence of liver metastases and/or progression of the underlying cancer.

Renal failure has been reported in five suspected cases to date. One patient with no alternative explanation made a complete recovery following study drug adjustment and no treatment/therapy for the event. The rest of the patients had concurrent morbidities, which might have contributed to the reported events.

Hypophosphatemia, hypomagnesemia, hyponatremia and hypocalcemia have been reported as serious adverse reactions. Electrolytes should be monitored in patients treated with everolimus.

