The probabilities of dose escalation for various true DLT rates are summarized below:

	True Probability of DLT at Current Dose						
	0.10	0.20	0.30	0.40	0.50	0.60	0.70
Probability that dose is escalated	0.91	0.71	0.49	0.31	0.17	0.08	0.03

Expansion cohort:

The primary objective is to evaluate the safety and efficacy of the combination of pazopanib and everolimus in previously treated advanced urothelial carcinoma patients. The proportion of patients achieving objective response (OR) defined as complete or partial response per RECIST criteria as their best overall response is the primary endpoint. Simon's two-stage design is employed to minimize accrual if treatment with pazopanib and everolimus is not effective. Achieving objective response in this population has historically been difficult. There no FDA approved second line therapy for urothelial cancer. The only European approved therapy in this setting is Vinflunine with a response rate of 9%.⁽⁴⁸⁾ The null hypothesis for this study is assumed to be 10%.

Twenty-nine patients will be enrolled. Only eligible patients who start protocol therapy will be included in the response analysis. The first stage will accrue n=20 patients (n=18 eligible treated patients). If 3 or more objective responses are observed among the first stage cohort then an additional 9 patients will be accrued (n=8 eligible treated patients). If 5 or more responses are observed in the 26 eligible patients who started protocol therapy

then the combination of pazopanib with everolimus will be considered promising. The operating characteristics of this design are summarized below. If the true OR rate is 10%, the probability of stopping early at the first stage is 0.734 and the probability of accepting treatment for further study is 0.099 (Type I error). If the true OR rate is 30%, the probability of concluding the treatment is promising is 0.904 (power). Upon completion of the study, the true response rate will be estimated and an exact 90% confidence interval constructed.

	True Underlying Response Rate				
			20%	25%	30%
Probability of Stopping Early (<3/18)			0.271	0.135	0.060
Overall Probability of Concluding Effective ($\geq 5/29$)			0.577	0.781	0.904

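### The expansion cohort has a stopping rule for response but no pre-set toxicity count that pauses enrolment, although 2 of 6 patients at its dose stopped for toxicity after the 28-day window that cleared the dose

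*Combined protocol and SAP*

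**What the plan says.** **Escalation.** Section 5.4.1 has a toxicity rule for the whole cohort. If two or more patients at dose level -1 have a DLT, "then the combination will be deemed not feasible and the study will be closed". Section 5.4.2 limits the event by phase and by time: "For the purposes of Phase I dose escalation, a DLT will be defined as toxicity occurring within the first 28 days of combination therapy".

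**Expansion.** Sections 5.1 and 6 set the expansion dose at level -1. Section 14.1 gives the only stopping rule: "Simon's two-stage design is employed to minimize accrual if treatment with pazopanib and everolimus is not effective". Enrolment continues past stage 1 with 3 or more responses among 18 eligible treated patients, and 5 or more among 26 make the combination promising. Section 14.4 tabulates grade 3 or higher toxicity with 90% confidence intervals and attaches no action to any count.

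**Size.** Section 14.1 states "Twenty-nine patients will be enrolled", and the toxicity table in 14.4 also uses 29. Sections 1.1 and 14.2 give 25.

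**Oversight.** Section 12.2 provides monthly calls between the two sites during the expansion and an independent committee: "The DSMC will meet quarterly and/or more often if required to review toxicity and accrual data". Items the committee may receive include DLT information, a summary of deaths within 30 days, a study-team summary and "all grade 2 or higher unexpected adverse events that have been reported". Sections 11.4 and 11.5 require serious adverse events to be reported within 24 hours.

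**Experience at this dose.** The Phase I update in Section 2.3 reports no DLT in six patients at level -1. It then adds: "Two of 6 patients came off treatment after 2 cycles because of toxicity".

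**The concern.** The protocol thought a written toxicity rule necessary for six patients at level -1. It then treats four to five times as many at the same dose without one. Section 14.1 makes safety as well as efficacy the expansion's primary objective (Section 1.3 lists safety as secondary), yet both decisions in the two-stage design, to continue and to call the regimen promising, depend on responses alone.

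The window adds to this. The dose was cleared on events in the first 28 days, while the reported toxicity stops came after two 28-day cycles. Carrying the DLT definition forward unchanged would not count such events. DLT information in the committee's packet also has no defined meaning in the expansion, because the definition is confined to dose escalation.

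At stake is how many patients enter before someone decides, without an agreed threshold, that too many are stopping for toxicity.

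**Working it through.** **1. The plan's own rule (14.1).** Inputs: n1 = 18, continue at 3 or more; n = 26, promising at 5 or more.

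- Early stop = P(X ≤ 2 of 18): 0.734 at a 10% response rate (stated 0.734).
- Promising = sum over x ≥ 3 of P(X1 = x of 18) × P(X2 ≥ 5 − x of 8): 0.099 at 10% and 0.904 at 30% (stated 0.099 and 0.904).

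The figures reproduce, and toxicity enters none of them. The chance of passing stage 1 is 1 − P(X ≤ 2 of 18) = 0.27, 0.73 and 0.94 at response rates of 10%, 20% and 30%, whatever the toxicity rate.

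**2. What six patients tell us (2.3).**

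- DLTs within 28 days, 0 of 6: one-sided 95% upper limit = 1 − 0.05^(1/6) = 0.393.
- Toxicity stops after 2 cycles, 2 of 6 = 33%: exact (Clopper-Pearson) 90% CI from the 5% point of Beta(2, 5) to the 95% point of Beta(3, 4) = 0.063 to 0.729.
- Timing: 2 × 28 = 56 days, against a DLT window of 28 days.

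**3. Patients affected if nothing prompts a pause.** The documents state no unacceptable rate, so these rates are assumed. Expected patients with an event:

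| Assumed rate | of 25 | of 29 |
|---|---|---|
| 20% | 5.0 | 5.8 |
| 33% (1/3) | 8.3 | 9.7 |
| 50% | 12.5 | 14.5 |

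**4. Accrual between reviews (14.2: 3 per month).** About 3 patients enter between monthly calls, and 3 × 3 = 9 between quarterly DSMC meetings.

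**5. Can a simple count work?** For illustration only, pause for review at 3/5, 5/10, 7/15, 9/20 or 11/25 patients with an event. The exact sequential binomial carries forward the distribution of counts below the boundary and adds the probability of first crossing at each look. At a 50% event rate the five contributions are 0.500, 0.187, 0.097, 0.059 and 0.039.

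| Assumed event rate | P(pause) |
|---|---|
| 20% | 0.08 |
| 30% | 0.29 |
| 33% | 0.38 |
| 40% | 0.62 |
| 50% | 0.88 |

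These figures ignore the response stop and patients enrolled while others are still in their observation window. With 29 patients, one more look would be needed after patient 25.

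**The case against.** The strongest answer is that oversight exists and is not weak. The monthly calls are there to monitor safety. The DSMC is independent and can meet off schedule. Serious events are reported within 24 hours, Section 6 has detailed stopping rules for individual patients, and Section 13.1 allows immediate safety action. All of this stands. A reader might infer that an intolerable regimen would have to enrol fully; the documents do not say that, since enrolment can be paused on judgement. What is missing is an agreed count that prompts the judgement.

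A reader might also infer that expected severe toxicity would be kept from the DSMC. Section 11.2.3.2 treats a listed event as unexpected when it departs from the listing in intensity or frequency, and the packet list is open-ended. The fair statement is narrower: grade 3 or higher events and toxicity discontinuations are not named items.

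The late-toxicity evidence has qualifiers. Section 6.1.1 says "The increase in transaminase's (AST and ALT) generally appears after 4 weeks of treatment", but adds that nearly all such rises stay within grade 1. The fatal pneumonitis at about two months was in a patient on 10 mg/day, and the death was considered possibly related to late-stage tumour as well as drug. Section 2.3 describes treatment at this dose as generally well tolerated. The case therefore rests on the 2 of 6, not on these.

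Finally, the example boundary is not calibrated to a 33% limit. At a true 33% it fails to pause 1 − 0.38 = 0.62 of the time. It shows feasibility only.

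**Conclusion.** The point holds as a gap in pre-specification. The dose has a toxicity closure rule in escalation and no cohort-level toxicity trigger in the expansion, where 25 or 29 patients receive it and the only formal rule counts responses.

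Setting 2 of 6 (33%) beside the <33% DLT limit in 14.1 might suggest that the limit was breached. It was not: that limit concerns events within 28 days, and the stops came later. Nor does 2 of 6 show that the dose is intolerable, since an interval of 6% to 73% fits both a tolerable and an intolerable regimen. What it shows is that toxicity serious enough to end treatment occurred after the window that cleared the dose, and 0 of 6 within that window still leaves room for a DLT rate up to 39%.

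This is a worthwhile, inexpensive improvement to patient protection rather than an error in the design's arithmetic, which reproduces. The size depends on the assumed event rate, because the documents give no rate they would regard as unacceptable.

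**What to change.** - **14.1 and 12.2:** bring the expansion into line with 5.4.1 by pre-specifying a cohort-level toxicity count that pauses enrolment for DSMC review. It should cover at least cycles 1-2 and every expansion patient, including those after patient 20. The study team and DSMC should choose the event, the unacceptable rate and the boundary, and print the operating characteristics beside the two-stage table.
- **12.2:** name treatment-related grade 3 or higher events, expected or not, and toxicity discontinuations as packet items.
- **1.1, 14.1, 14.2 and 14.4:** reconcile 25 with 29, so that the last look covers the last patient.

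The cost is amendment wording and a running count from forms already due under 12.1.2 (adverse events within 10 days of each cycle's end, off-treatment within 14 days). No new committee is needed. The downside is an unneeded temporary pause. With the example boundary that chance is about 8% if the event rate is 20% and 29% if it is 30%, so a broadly defined event would pause more often. No dose or individual treatment rule is proposed.
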